### 3.0 OBJECTIVES AND ENDPOINTS

Objectives	Endpoints
Primary	

To evaluate preliminary safety and efficacy of oral decitabine/cedazuridine in combination with magrolimab.

	

Adverse events graded according to NCI CTCAE, Version 5.0 (Section 10.5), DLTs, and CR rate.

Secondary	

To evaluate the PK profile of oral decitabine/cedazuridine and magrolimab.

	

Concentration versus time and PK parameters.

To evaluate other clinical efficacy of oral decitabine/cedazuridine and magrolimab.

	

ORR, rate of HI, duration of PFS, LFS, undetectable disease assessed by MRD, DOR, and OS.

To evaluate efficacy and safety by prespecified subgroups (eg, IPSS-M, p53 status).

	

Safety and efficacy based on molecular features (eg, IPSS-M score, p53 status).

CR=complete response; DLT=dose-limiting toxicity; DOR=duration of response; HI=hematologic improvement; IPSS-M=Molecular International Prognostic Scoring System for myelodysplastic syndromes; LFS=leukemia-free survival; MRD=minimal residual disease; NCI CTCAE=National Cancer Institute Common Terminology Criteria for Adverse Events; ORR=overall response rate; OS=overall survival; PFS=progression-free survival; PK=pharmacokinetic(s)

### 4.0 STUDY DESIGN

#### 4.1 Overall Design

This is a Phase 2, open-label, multicenter, non-randomized interventional study to evaluate the safety, efficacy, and PK of oral decitabine/cedazuridine when given in combination with magrolimab for the treatment of subjects with previously untreated intermediate- to very high-risk MDS. Subjects with higher-risk MDS (IPSS-R  $\geq 3.5$ ) will be screened for participation with the goal of obtaining approximately 100 subjects who are evaluable, those subjects receiving one or more dose of study treatment, for the primary study endpoint. The first 6 to approximately 18 subjects enrolled will be evaluated for dose-limiting toxicities (DLTs) during the first 2 cycles of oral decitabine/cedazuridine and will be used to confirm the dosing for oral decitabine/cedazuridine in combination with magrolimab. In this protocol, a cycle is defined as a

cycle of oral decitabine/cedazuridine, which is normally 28 days. Dose-limiting toxicities are defined in Section 8.5.6.

The primary analysis of the CR rate will be conducted approximately 8 months after enrollment of approximately 100 subjects has occurred. Participation will include screening, treatment, and follow-up. The screening period will last up to 21 days before the first dose of study treatment, during which time the participant's eligibility and baseline characteristics will be determined. Subjects will receive study treatment per the dosing schedule in [Table 3](#) and [Table 4](#). Study treatment may be continued until disease progression (including treatment failure by the International Working Group [IWG] 2006 criteria or relapse after PR/CR), or unacceptable toxicities occur, the subject is withdrawn from study treatment, or the sponsor stops the study. In case subjects choose to discontinue the study treatment due to reasons other than disease progression, eg, voluntary withdrawal, subjects will be followed up for response assessments until documented disease progression occurs. For subjects who stop receiving the study treatment to receive a stem cell transplant (SCT), follow-up for response assessment and collection of SOC BM biopsy/aspirate results will continue until documented disease progression occurs or start of new anticancer therapy, whichever occurs first. Then subjects will be observed for survival until death, withdrawal of consent, or the end of the study, whichever occurs first.

The study duration will be approximately 44 months. This may be adjusted based on enrollment rate as well as DOR.

The Schedules of Activities (SoAs) are detailed in [Table 1](#) and [Table 2](#).

The COVID-19 pandemic may continue to affect the way clinical studies need to be conducted such that alternative measures may need to be implemented to ensure the safety of subjects and maintain the integrity of clinical trial data. Section 10.7 details information regarding potential modifications to the conduct of the study in the event of a COVID-19 health emergency.

#### 4.1.1 Dose-Limiting Toxicity Cohort

[figure not shown]
The first 6 to approximately 18 subjects enrolled, the DLT cohort, will be evaluated to confirm that the dosing of oral decitabine/cedazuridine in combination with magrolimab is well tolerated (Section 8.5.6). Due to the low incidence of magrolimab DLTs (please reference Investigational New Drug [IND] 147229 for the magrolimab Investigator Brochure), it is expected that most DLTs will be related to oral decitabine/cedazuridine, especially those related to neutropenia, thrombocytopenia, GI toxicity, and infection. Thus, a DLT should generally be considered related to oral decitabine/cedazuridine unless the investigator feels that a DLT is related to magrolimab. The DLT period will last the first 2 cycles of oral decitabine/cedazuridine treatment as defined in Section 4.1. Evaluation of the cohort will end when a tolerated dosing is identified, or the study is stopped due to toxicity. Oral decitabine/cedazuridine and magrolimab dosing will initiate as outlined in Section 4.5. If there are DLTs associated with magrolimab that occur in the DLT cohort, the investigator in consultation with the Astex medical monitor and the Data and Safety

Review Committee (DSRC) will determine if a dose modification of magrolimab is appropriate (see Section [6.6.2](#) for magrolimab dose modification recommendations).

The dosing reduction process for oral decitabine/cedazuridine-associated DLTs will follow a 3+3 design ([Figure 2](#)), as follows:

- The first 6 subjects will be evaluated for myelosuppression and other DLTs (Section [8.5.6](#)).
- If fewer than 2 subjects among the first 6 (<33%) experience a DLT (Section [8.5.6](#)), the current dosing level will be maintained, and no further DLT cohort evaluation will be conducted.
- If a DLT occurs in 2 or more of the initial 6 subjects, then oral decitabine/cedazuridine dosing will be reduced 1 level ([Table 9](#)) and 3 more subjects will be enrolled at that dosing level.
- If no additional DLTs occur, the dosing will be maintained, and no further DLT cohort evaluation will be conducted. If any DLT occurs, another 3 subjects will be enrolled. If fewer than 2 subjects (<33%) have a DLT out of the 6 subjects, then the dosing will be maintained, and no further DLT cohort evaluation will be conducted. If oral decitabine/cedazuridine associated DLTs occur in 2 or more out of 6 subjects, dosing of oral decitabine/cedazuridine will be reduced one dose level as per [Table 9](#), and 3 more subjects will be enrolled.
- This process is repeated until a tolerated oral decitabine/cedazuridine dosing is identified and the dosing will be maintained with no further DLT cohort evaluation OR the dosing levels falls to Level 5 ([Table 9](#)) and in consultation with the DSRC, the study will be closed or the protocol amended to modify the dosing of oral decitabine/cedazuridine.
- During the study, a stopping rule for observation of excess toxicity will be implemented, as described in Section [9.5](#).

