#### **Data Safety Review Committee and Safety Monitoring Plan:**

The Data and Safety Review Committee (DSRC) will comprise the principal investigators (or designees), and the Astex medical monitor, clinical pharmacologist, lead statistician, and other study team members as appropriate.

The DSRC will review emerging safety data after the first 6 subjects are enrolled. The first 6 to approximately 18 subjects enrolled will be evaluated for DLTs during the first 2 cycles; if present (following standard 3+3 design), there will be dosing reductions of oral decitabine/cedazuridine which will be applied to all subsequent subjects. In addition, the DSRC will continue to review safety data after approximately 20 subjects are enrolled and receive at least 2 cycles of treatment. Ad hoc meetings may occur throughout the study.

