#### **4.3 Data and Safety Review Committee**

The DSRC will comprise the principal investigators (or designees), and the Astex medical monitor, clinical pharmacologist, and lead statistician, and other study team members as appropriate.

The DSRC will review emerging safety data after the first 6 subjects are enrolled. The first 6 to approximately 18 subjects enrolled will be evaluated for DLTs during the first 2 cycles; if present (following standard 3+3 design), there will be dosing reductions of oral decitabine/cedazuridine which will be applied to all subsequent subjects.

Further details of the DLT cohort are provided in Section [4.1.1](#).

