#### **8.5.6 Definition of Dose-limiting Toxicities**

Dose-limiting toxicities are defined as any of the following toxicities at least possibly related to the treatment regimen as determined by the DSRC:

- Drug-related Grade  $\geq 3$  non-hematologic events (except nausea, vomiting, or diarrhea if the events do not require tube feeding, total parenteral nutrition, or require or prolong hospitalization).
- Grade 4 neutropenia and thrombocytopenia, not present prior to dosing, that last 28 days or longer should be considered a DLT unless clearly and solely due to the underlying disease.

- If the investigator suspects that the development of Grade 4 neutropenia or thrombocytopenia is drug related and the event continues for 7 days in Cycle 1, a BM assessment (no later than the 14th day of Grade 4 cytopenia) may be done, at the discretion of the investigator, to assist with the determination of DLT.
- Delay of >2 weeks after Cycle 1 is complete due to drug-related toxicity. That is, if initiation of Cycle 2 is delayed for drug-related toxicity, the DLT window will expand accordingly.
- Establishment of an MTD is not a goal of this study. However, the DSRC will assess the occurrence of DLTs in the DLT cohort (Section 4.1.1) to help ensure the study drug combination is safe. The DLT period has been defined as the first 2 cycles of oral decitabine/cedazuridine (from the start of administration to Cycle 1 Day 28) in the first 6 to approximately 18 subjects.

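### Minor safety-wording error in Section 4.1.1: at a reduced level, two of the first three subjects with oral decitabine/cedazuridine-associated DLTs still lead to three more, although reduction is then unavoidable

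*Combined protocol and SAP*

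**What the plan says.** Section 4.1.1 treats six subjects at the starting dosing and reduces one level if two or more have a DLT. Each reduced level begins with three subjects. With no DLT among them the dosing is kept. Otherwise: "If any DLT occurs, another 3 subjects will be enrolled". The dosing is then kept "If fewer than 2 subjects (<33%) have a DLT out of the 6 subjects", and the level fails if oral decitabine/cedazuridine "associated DLTs occur in 2 or more out of 6 subjects, dosing of oral decitabine/cedazuridine will be reduced one dose level". The text has no separate branch for two or three DLTs among the first three.

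Other provisions bear on this:

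- Section 4.1.1 points to Section 9.5: "During the study, a stopping rule for observation of excess toxicity will be implemented". Table 17 gives the boundary on the cumulative number of subjects with DLTs.
- On attribution, Section 4.1.1 says that "a DLT should generally be considered related to oral decitabine/cedazuridine unless the investigator feels that a DLT is related to magrolimab".
- Section 4.3 describes the scheme as dose reduction for DLTs "if present (following standard 3+3 design), there will be dosing reductions of oral decitabine/cedazuridine".
- Table 9 lists four active levels: Daily×5, Daily×4, Daily×3, and Days 1, 3 and 5.
- Figure 2 depicts the reduction process, but its content was not available for review.

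**The concern.** The second group of three exists to settle a level that the first three left undecided. One DLT in three leaves it undecided. Two DLTs in three, both associated with oral decitabine/cedazuridine, do not: whatever follows, the level ends with at least two of six and is reduced. Followed literally, the text still treats up to three further subjects at that level.

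At stake is the dose those subjects receive. At Level 2 they would get Daily×4 instead of Daily×3. At Level 3 they would get three consecutive days instead of Days 1, 3 and 5. Their outcomes add nothing to the decision on the level, although their DLTs would count toward the Section 9.5 total, as would those of subjects treated one level lower.

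**Working it through.** **Inputs.** Section 4.1.1: Level 1 has six subjects and is reduced at two or more DLTs; Levels 2 to 4 have three subjects, are kept at none, otherwise add three, and are reduced at two or more of six. Table 17 boundaries: n=2: 2; 3-4: 3; 5-7: 4; 8-10: 5; 11-14: 6; 15-17: 7; 18-21: 8. The DLT rate p of the combination is not given and is assumed, with q = 1−p.

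**1. The plan's own figure.** An exact recursion through Table 17 (n=2 to 100) gives a crossing probability of 0.199 at a 20% DLT rate. This agrees with the ceiling of 20% stated in Section 9.5.

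**2. Logic.** With x ≥ 2 associated DLT subjects in the first three and y = 0 to 3 in the next three, x + y ≥ 2 always. Over all 64 outcomes of six subjects, reducing at once gives the same keep-or-reduce decision as the current text (0 differences).

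**3. Does Section 9.5 pre-empt it?**

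| Path | Cumulative | Boundary | Result |
|---|---|---|---|
| 2/6, then 2/3 at Level 2 | 4/9 | 5 | continues |
| 3/6, then 2/3 at Level 2 | 5/9 | 5 | halts |
| 2/6, then 3/3 at Level 2 | 5/9 | 5 | halts |
| 2/6, 2/6, then 2/3 at Level 3 | 6/15 | 7 | continues |
| 2/6, 2/6, then 3/3 at Level 3 | 7/15 | 7 | halts |
| 2/6, 2/6, 2/6, then 2/3 at Level 4 | 8/21 | 8 | halts |

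One more DLT at any earlier level also halts, so only the two continuing paths survive.

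**4. Chance of enrolment at a level bound to fail** (same p at all levels, boundary checked after each subject).

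- Level 2 path: 2 of 6 has 15 orders; the boundary of 2 at n=2 removes one, leaving 14. Then 2 of 3 has 3 orders. A = 14×3×p⁴q⁵ = 42p⁴q⁵.
- Level 3 path: 14 orders at Level 1. At Level 2, 2 of 6 with at least one in the first three has 15−3 = 12 orders. At Level 3, 2 of 3 has 3 orders, but both in the first two gives 6/14 against 6 and halts, leaving 2. B = 14×12×2×p⁶q⁹ = 336p⁶q⁹.
- Trials meeting both: C = 14×3×2×p⁶q⁹ = 84p⁶q⁹.
- Chance = A + B − C.

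At 20%: 0.02202 + 0.00289 − 0.00072 = 0.0242. At 30%: 0.05718 + 0.00988 − 0.00247 = 0.0646.

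**5. Expected subjects affected.** After 4/9, a DLT in subject 10 gives 5/10 against 5 and halts; otherwise all three are enrolled: p + 3q. After 6/15, a DLT in subject 16 or 17 halts at 7: p + 2pq + 3q².

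At 20%: 0.02202×2.6 + 0.00289×2.44 = 0.064. At 30%: 0.05718×2.4 + 0.00988×2.19 = 0.159.

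| Assumed DLT rate | Chance | Expected subjects |
|---|---|---|
| 10% | 0.3% | 0.01 |
| 15% | 1.0% | 0.03 |
| 20% | 2.4% | 0.06 |
| 30% | 6.5% | 0.16 |
| 40% | 9.4% | 0.21 |

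**6. Sensitivity.** With rates falling over Levels 1 to 4, the chance and expected subjects are 1.4% and 0.04 (20/15/10/10%), 4.6% and 0.12 (30/25/20/20%), and 5.8% and 0.14 (40/30/20/20%). If each DLT subject is attributed to magrolimab with probability 10% or 20%, the chance falls to 1.9% or 1.5% at a 20% rate, and to 5.1% or 4.0% at 30%. Only DLTs in the evaluation window are counted; later events also count under Section 9.5 and could only halt accrual sooner.

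**The case against.** The best defence is that the rule is more than one sentence. Figure 2 is part of it and may show the missing branch. Sections 1.1 and 4.3 call the scheme a standard 3+3, which a reader may take to end a level at two of three. DLTs are those "at least possibly related to the treatment regimen as determined by the DSRC", and the Synopsis adds: "Ad hoc meetings may occur throughout the study". The sponsor may stop enrollment for safety. Section 9.5 is mandatory and removes most cases. The trial treats about 100 subjects regardless, so those affected would be enrolled anyway, one level lower, and every reduced level lies below the approved Daily×5 regimen.

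Much of this stands, and it is why the point is minor. It does not remove the point. The explicit sentence in 4.1.1 says to enrol three more after any DLT, and a general label does not override it. The committee's and sponsor's powers are discretionary. If Figure 2 does show the branch, text and figure disagree and need aligning.

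Attribution also matters. If one of two DLTs is ascribed to magrolimab, reduction is not yet certain and three more subjects are reasonable.

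**Conclusion.** The text contains a minor safety-wording error. After two of the first three subjects at a reduced level have associated DLTs, reduction is certain, yet three more are to be enrolled. Section 9.5 leaves two paths open. The chance is about 2.4% at a 20% DLT rate and 6.5% at 30%, with 0.06 and 0.16 subjects expected. These figures rest on assumed rates, equal across levels, all DLTs attributed to oral decitabine/cedazuridine, and literal use of the text.

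A reader might infer more than the documents support:

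- *That the reduction criterion is formally met at two of three.* It is written for six subjects; at two of three it is unavoidable rather than evaluated.
- *That the wrong dose could be selected or extra subjects recruited.* The keep-or-reduce decision never changes, and the planned total of about 100 is unaffected.
- *That the chance of two or more DLTs in three (10.4% at a 20% rate) measures the effect.* That figure assumes a reduced level has been opened and ignores Section 9.5.
- *That the whole plan lacks the branch.* Figure 2 could not be seen, so the finding concerns the text only.

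**What to change.** Check Figure 2 first and make text and figure agree. In Section 4.1.1, state for each reduced level:

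- no subject among the first three with a DLT: keep the dosing;
- two or more of the first three with an oral decitabine/cedazuridine-associated DLT: close the level and reduce one level at once;
- any other result with a DLT, including two subjects of whom one has a DLT attributed to magrolimab: enrol three more, as now;
- the Section 9.5 boundary takes precedence throughout.

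The cost is protocol wording only. No subjects are added and no dose level is lost. With Section 9.5 applied, the expected DLT-cohort size moves from 7.29 to 7.23 at a 20% DLT rate and from 7.99 to 7.87 at 30%.

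### The 3+3 rule in Section 4.1.1 counts DLTs from either drug in some branches and only oral-drug DLTs in another, so some results have no stated action or two competing ones

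*Combined protocol and SAP*

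**What the plan says.** All the decision text is in protocol Section 4.1.1, with the DLT definition in Section 8.5.6.

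- **Scope.** The sentence introducing the bullets reads "The dosing reduction process for oral decitabine/cedazuridine-associated DLTs will follow a 3+3 design". The title of Figure 2 carries the same restriction to oral-drug DLTs.
- **Initial 6 subjects, maintain.** "If fewer than 2 subjects among the first 6 (<33%) experience a DLT", with a reference to Section 8.5.6.
- **Initial 6 subjects, reduce.** "If a DLT occurs in 2 or more of the initial 6 subjects, then oral decitabine/cedazuridine dosing will be reduced 1 level".
- **Reduced level, going from 3 to 6 subjects.** "If any DLT occurs, another 3 subjects will be enrolled".
- **Reduced level, maintain.** "If fewer than 2 subjects (<33%) have a DLT out of the 6 subjects, then the dosing will be maintained".
- **Reduced level, reduce.** "If oral decitabine/cedazuridine associated DLTs occur in 2 or more out of 6 subjects, dosing of oral decitabine/cedazuridine will be reduced one dose level".

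Section 8.5.6 defines a DLT as one of the listed toxicities that is "at least possibly related to the treatment regimen as determined by the DSRC", so an event caused by either drug can qualify. Section 4.1.1 assigns a DLT to the oral drug by default, "unless the investigator feels that a DLT is related to magrolimab". It expects most DLTs to be oral-related. It sends magrolimab DLTs to a separate decision by the investigator, the medical monitor and the DSRC. It does not say whether those events also count in the 3+3 tally.

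**The concern.** A dose-finding rule should give exactly one action for every result that can occur. Here two adjacent sentences for the reduced level use different counts, so they do not cover all results between them. For the initial 6, the bullets agree with each other but not with the sentence that introduces them.

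The stake is the oral dose for the rest of the study. Sections 4.3 and 9.5 apply whatever the DLT cohort produces to all subsequent subjects, out of about 100. If an undetermined result occurs, the action would have to be settled after the data are known, in an open-label study, by a committee of investigators and sponsor staff (Section 4.3).

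**Working it through.** **The plan's own figure.** The maintain branches attach <33% to fewer than 2 of 6. Since 1/6 = 16.7% and 2/6 = 33.3%, the figure is right.

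**Coverage of the rule.** Let t be the number of subjects out of 6 with any DLT, and o the number with an oral-associated DLT, with 0 ≤ o ≤ t ≤ 6. There are 1+2+…+7 = 28 possible pairs.

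- Initial 6, bullets as worded: maintain if t < 2, reduce if t ≥ 2.
- Initial 6, lead-in scope: maintain if o < 2, reduce if o ≥ 2.
- Reduced level as worded: maintain if t < 2, reduce if o ≥ 2.

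The readings differ, or no branch applies, when t ≥ 2 and o ≤ 1. That is t = 2 to 6 with o = 0 or 1, or 5 × 2 = 10 of the 28 pairs. In those pairs:

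- in the initial 6, the bullets say reduce and the lead-in implies maintain;
- at a reduced level, neither condition is met.

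No pair satisfies both maintain and reduce at a reduced level, because t < 2 and o ≥ 2 cannot both hold.

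**Size: inputs.** The per-subject DLT rate is p = 0.20, the rate presumed for the stopping boundary in Section 9.5. The share f of subjects with a DLT whose DLTs are all attributed to magrolimab is not in the documents; I assume 5%, 10%, 25% and 50%. Then the oral-associated rate is p_o = p(1 − f). Subjects are taken as independent, and p is taken as unchanged at the reduced level.

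**Initial 6.** With P_n(q) = 1 − (1 − q)^n − nq(1 − q)^(n−1), the chance of 2 or more out of n:

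P(t ≥ 2 and o ≤ 1) = P_6(p) − P_6(p_o), because o ≥ 2 implies t ≥ 2.

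P_6(0.20) = 1 − 0.2621 − 0.3932 = 0.3446.

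**Reduced level.** The cohort reaches 6 only if at least one of the first 3 has a DLT, so subtract the cases with none:

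P(gap) = [P_6(p) − P_6(p_o)] − 0.8³ × [P_3(p) − P_3(p_o)], with 0.8³ = 0.512 and P_3(0.20) = 0.1040.

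| f (assumed) | p_o | P_6(p_o) | Initial-6 conflict | P_3(p_o) | Subtracted | Gap at reduced level |
|---|---|---|---|---|---|---|
| 5% | 0.19 | 0.32008 | 0.02456 (2.5%) | 0.09458 | 0.00482 | 0.01974 (2.0%) |
| 10% | 0.18 | 0.29559 | 0.04905 (4.9%) | 0.08554 | 0.00945 | 0.03959 (4.0%) |
| 25% | 0.15 | 0.22352 | 0.12112 (12.1%) | 0.06075 | 0.02214 | 0.09898 (9.9%) |
| 50% | 0.10 | 0.11427 | 0.23038 (23.0%) | 0.02800 | 0.03891 | 0.19146 (19.1%) |

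The gap figures are conditional on a reduced-level cohort being opened. Counting any DLT, that happens after the initial 6 with probability 0.3446. The chance of meeting the gap at the first reduced level is then 0.3446 × 0.01974 = 0.7% at f = 5%, and 0.3446 × 0.03959 = 1.4% at f = 10%.

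**After repair.** With one count throughout, all 28 pairs fall in exactly one branch. The choice of count still matters: the chance of reducing after 6 subjects is 34.5% counting any DLT. Counting only oral-associated DLTs, it is 32.0%, 29.6%, 22.4% and 11.4% for the four shares.

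**The case against.** The best defence is that the lead-in governs every bullet, so that each mention of a DLT below it is shorthand for an oral-associated one. On that reading each count out of 6 has one action. It is a natural reading, but the text does not compel it. Section 4.1.1 refers to the regimen-wide definition in Section 8.5.6, and only one branch repeats the oral-drug qualifier, which would then be redundant. The body of Figure 2 is not visible in the copy reviewed, so it may or may not settle the point; the text would have to match it either way.

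It can also be said that the outcome is infrequent. That stands. Section 4.1.1 calls magrolimab DLTs uncommon, expects most DLTs to be oral-related, and attributes them to the oral drug by default. This lowers the frequency but does not close the gap.

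Four stronger readings are tempting, and the documents do not support them.

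- *A level where most subjects have magrolimab DLTs would simply be maintained.* Section 9.5 counts DLT-criteria events at least possibly related to study treatment, whichever drug caused them. Its boundary is 4 for 5 to 7 subjects, so 4 of the initial 6 would halt accrual. Magrolimab DLTs also go to the DSRC, and Section 6.6.2 covers magrolimab modification. These limit the safety consequence; they do not settle the oral dose decision.
- *The missing branch also affects the initial 6.* It does not. There, two DLTs of any attribution mean reduce as worded, and the conflict comes only from the lead-in and the Figure 2 title.
- *The investigator and the DSRC are rival judges of the same question.* Section 8.5.6 asks whether an event is related to the regimen; Section 4.1.1 asks which drug caused it. These can be answered in sequence.
- *The problem arises in 11% to 24% of cohorts.* Such figures follow from oral/magrolimab-only rates of 10%/5%, 10%/10% or 15%/10%, which make 33% to 50% of subjects with a DLT magrolimab-only. That sits poorly with the protocol's expectation.

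**Conclusion.** The concern holds as an inconsistent decision rule, of moderate severity. At a reduced level, 2 or more of 6 subjects with DLTs and at most one oral-associated has no stated action. This follows directly from two adjacent sentences if a DLT is read as Section 8.5.6 defines it. In the initial 6 the same result is assigned to reduce by the bullets and to maintain by the stated scope of the process.

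If magrolimab-only DLTs are as uncommon as the protocol expects (taken here as a 5% to 10% share), the conflict arises in about 2.5% to 4.9% of initial cohorts and the gap in about 2.0% to 4.0% of reduced-level cohorts. The higher values in the table need shares of 25% to 50%, which the documents do not suggest. All these figures rest on the 20% rate, the assumed shares, independence between subjects and an unchanged rate at the reduced level. The inconsistency itself rests on none of them.

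**What to change.** Reconcile the lead-in sentence, all bullets in Section 4.1.1, Figure 2 and the reference to Section 8.5.6, so that:

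1. every branch at every dose level uses one stated count, either all regimen-related DLTs or oral-associated DLTs;
2. each result out of 3 and out of 6 maps to exactly one action;
3. the text says whether DLTs attributed to magrolimab enter that count.

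Which count governs is for the sponsor and DSRC to decide. A separate numerical trigger for magrolimab DLTs would be a design preference and is not needed to repair the inconsistency.

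The cost is a clarification of one section and one figure, best made before the DLT cohort is read. It needs no added subjects.
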